2. RESEARCH PROTOCOL

PURPOSE OF THE STUDY

The purpose of the present study is to better understand the impact of visual impairment on daily task performance in patients with eye diseases and diseases of the visual pathways, such as glaucoma and age-related macular degeneration (AMD).

BACKGROUND & SIGNIFICANCE

Glaucoma is a progressive optic neuropathy that may result in significant visual impairment. The loss of vision affects the quality of life and also has economic consequences to the patient and to society.¹ The fundamental goal of glaucoma management is to prevent patients from developing visual impairment sufficient to produce disability in their daily lives and impair their health-related quality of life (HRQOL). Although investigations of glaucoma diagnostics have focused largely on conventional testing with perimetry and optic nerve evaluation, there is a compelling need to better characterize measures of functional impairment and HRQOL in glaucoma and to understand how they relate to conventional clinical tests. Our previous results have shown important relationships between subjective measures of disability obtained through patient-reported outcomes and metrics of structural and functional damage in the disease. However, self-reported evaluations are based on each individual's assessment of his or her ability to do a particular task and can be largely influenced by personal expectations, understanding of the degree of difficulty involved, personality and emotions, and may not correspond well to objective measures of performance. Therefore, an assessment of disability in glaucoma and other eye diseases necessarily involves an understanding of how the disease objectively affects patient performance on tasks, such as searching for

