Virtual reality tests will be conducted using virtual reality goggles (HTC Vive, Samsung Gear VR or FOVE). The tasks include scenarios replicating daily activities such as driving through a road, walking through a virtual environment or searching for objects. In order to navigate through the environment, subjects will use a steering wheel or joystick. The estimated duration of the test is 30 minutes. In the task of navigation, the subject will find him or herself near a wall in a rectangular room with colored walls, different objects on each wall, and different objects (couch, table statue, etc.) at various locations. The subject will be asked to move to and step upon a green tile that is displayed at some random location in the room. Once the target location is attained, the display is turned off for a short period. The task will then begin again, but with a different starting position. These initial tests are designed to assess the subject's ability to move from one location to another in a virtual environment. Subjects that can achieve sufficient proficiency in the target-visible protocols will then be instructed that the next series of tests will require them to find a hidden target tile and that they will be asked to remember its location. In these protocols, the subjects will be given a limited amount of time (2 minutes) to locate the target, which will become visible when it is reached, and their path and time to target discovery recorded. Path length and path topology will be measured in real time. The test will be repeated, from the same starting location, at least 5 times or until no improvement in time/distance to target is observed by the experimenter, who is analyzing the test outcomes on a tablet in real time. After a 5-minute rest period with no visual stimulus, the subject will be asked to repeat the task for a "probe" trial. This time the search will be limited to 30 seconds or to the shortest time attained in the prior trials, without the target becoming visible. The outcome measurement will be time spent and path length in the vicinity of the target, as a measure of spatial memory and spatial navigation strategy. Depending on the data obtained in this set of trials, the subject will be asked to continue with further tests of increasing difficulty,

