as for example with reduced numbers of distinct landmarks or with random starting locations for a constant target position. Visual search task will consist of a virtual environment (e.g., an apartment) and the patient will be given a specific task of object finding. The time and path to complete the task will be obtained. For driving tasks, the subject will use a driving wheel to guide a car through a virtual environment and complete a simple task of wayfinding, following a car or negotiating a curve.

Balance Assessment:

During this test subjects will stand on a force platform while different visual stimuli will be presented. The force platform (AMTI Optima Human Performance System, Advanced Mechanical Technology, Inc., Watertown, MA) is used to evaluate the posture and balance by recording pressure changes at the four corners of the platform that change as the subjects stabilize themselves. For this test we will use virtual reality goggles (Oculus Rift, Oculus VR, LLC, Irvine, CA) to deliver the visual stimuli. Such a system is appealing since it provides whole-eye coverage allowing a controlled environment for the visual input. The subject will be required to fixate the gaze at the center of the scene, while different visual stimuli will be presented, such as rotating rings. A harness system (Handrail and Harness Safety Structure, Bertec Corp., Columbus, OH) will be used to prevent subjects from falling. The experiment will consist of a number of short (approximately 1 minute) sessions with pauses to rest in between. The total duration of the test will be approximately 20 minutes.

Retinal metabolic analysis:

The OcuMet Beacon is a novel medical device that non-invasively assesses retinal mitochondrial dysfunction. The device takes an infrared fundus image that highlights the acquisition area for the retinal metabolic image, takes a retinal flavoprotein fluorescence (FPF) metabolic image, and provides quantitative analysis of the retinal mitochondrial function and patient report printout.

Assessment of intraocular pressure (IOP) with Tono-Vera:

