Subjects will be referred from the Duke Eye Center care providers after a comprehensive clinical eye examination from a routine visit. If the last clinical eye examination is not within 6 months of the study visit, the participant will be examined by the PI, with no additional cost to the patient. Participants will also undergo other tests that will allow a better understanding of the relationship between potential visual impairment caused by their diseases and the ability to perform daily tasks. The results of the study are likely to provide important information on how eye diseases are associated with visual impairment, task performance and quality of life. This may lead to development of better tests to predict patient performance and visual loss, which could benefit patients with these diseases.

COSTS TO THE SUBJECT

All procedures described here, including both visits, will be free of charge to patients. There is no additional cost for the subject if they participate in the study. Study related activities/procedures will be paid by the study.

DATA ANALYSIS & STATISTICAL CONSIDERATIONS

Describe endpoints and power calculations. Provide a detailed description of how study data will be analyzed, including statistical methods used, and how ineligible subjects will be handled and which subjects will be included for analysis. Include planned sample size justification. Provide estimated time to target accrual and accrual rate. Describe interim analysis including plans to stop accrual during monitoring. Phase I studies, include dose escalation schema and criteria for dose escalation with definition of MTD and DLT.

For all test results and variables, an extensive data preparation will be performed, with analysis of distributions, error checking and cross-tabulation. We will investigate differences in the results of the tests between diseased and healthy participants. Normality of variables will be assessed using histograms and Shapiro-Wilk tests. Student t tests will be used for comparison of means of normally distributed variables, whereas Mann-Whitney tests will be used for non-normally distributed variables. Generalized estimating equations (GEE) will be used to take into account potential correlations between tests results from the two eyes of the same subject.

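### The hidden-target navigation outcome exists only for subjects who pass an undefined proficiency check, and the plan has no analysis rule for those who do not; if failure is commoner with worse vision, the disease difference is likely to be attenuated.

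*Combined protocol and SAP*

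**What the plan says.** Under Virtual Reality Tests, the navigation task begins with a visible tile that the subject must reach by steering wheel or joystick. The stated purpose of this stage is narrow: "These initial tests are designed to assess the subject's ability to move from one location to another in a virtual environment". Progress then depends on performance: "Subjects that can achieve sufficient proficiency in the target-visible protocols will then be instructed" that the next trials use a hidden tile. The protocol does not say what counts as sufficient, and it states no time or attempt limit for the visible stage.

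For the hidden-target trials, capped at 2 minutes, the target is one "which will become visible when it is reached, and their path and time to target discovery recorded". After a rest comes the probe trial, which carries the named outcome: "The outcome measurement will be time spent and path length in the vicinity of the target, as a measure of spatial memory and spatial navigation". A subject who is not passed to the hidden-target trials therefore has no value for this outcome.

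The analysis section (Data Analysis & Statistical Considerations) says: "We will investigate differences in the results of the tests between diseased and healthy participants". It names t tests or Mann-Whitney tests, GEE for the two eyes, mixed models for longitudinal data, and survival and joint models in general terms. None of these is tied to subjects without a hidden-target score. Nothing assigns them a value or rank, or says that they will be counted.

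**The concern.** The study's purpose is to "better understand the impact of visual impairment on daily task performance in patients with eye diseases", and the background section names moving through an environment as one of the tasks of interest. Inability to reach a displayed tile among furniture could itself be a sign of disability on that task. Under the plan it leads to a missing outcome and not to a poor one.

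The missing values follow from a rule in the protocol and depend on performance in the same family of tasks. If visual loss makes failure more likely, the diseased arm loses more of its weaker performers than the healthy arm does, and the two sets of completers look more alike than the two groups really are. The same could happen over time. Subjects in the disease arms repeat the full battery at later visits, so one who worsens could fail the check for the first time and drop out of the navigation trajectory at the point where decline is greatest.

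**Working it through.** The documents give no sample size, effect size, SD, pass rate or correlation for this task, so there is no planned figure to reproduce. Everything below is an illustration from assumed values.

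**Model.** Let V be proficiency with the visible target and Y the hidden-target outcome, both scored so that higher is better, normal with SD 1 in each arm and with correlation r. A subject has Y only if V exceeds a common cut-off. If a fraction p of an arm fails, the completers' mean of V lies above the full-arm mean by

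L(p) = φ(z_p) / (1 − p), where z_p is the normal quantile at p.

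Their mean of Y rises by r × L(p). Hence

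observed difference = true difference − r × [L(p diseased) − L(p healthy)].

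**Selection terms.**
- p = 5%: 0.1031 / 0.95 = 0.109
- p = 10%: 0.1755 / 0.90 = 0.195
- p = 12.6%: 0.2071 / 0.874 = 0.237
- p = 20%: 0.2800 / 0.80 = 0.350
- p = 30%: 0.3477 / 0.70 = 0.497

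**Case A: disease shifts the visible stage by the same 0.5 SD as the outcome.** With 5% of healthy subjects failing, the cut-off is −1.645. The diseased failure rate is Φ(−1.645 + 0.5) = Φ(−1.145) = 12.6%. With a true difference of 0.5 and r = 0.6:
0.5 − 0.6 × (0.237 − 0.109) = 0.42 SD, which is 15% too small. At r = 0.3 and 0.9 it is 0.46 and 0.38 SD (8% and 23% too small).

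**Case B: diseased failure rate set directly, 5% of healthy failing, r = 0.6.**

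| Diseased failing | Observed difference | Implied visible-stage shift |
|---|---|---|
| 10% | 0.5 − 0.6 × 0.086 = 0.45 SD | −1.282 + 1.645 = 0.36 SD |
| 20% | 0.5 − 0.6 × 0.241 = 0.36 SD | −0.842 + 1.645 = 0.80 SD |
| 30% | 0.5 − 0.6 × 0.388 = 0.27 SD | −0.524 + 1.645 = 1.12 SD |

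At 20% failing, correlations from 0.4 to 0.8 give 0.40 to 0.31 SD. The last column matters: a 20% failure rate presumes that disease harms reaching a visible tile by 0.80 SD while harming the navigation outcome by only 0.5 SD.

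**Case C: no attenuation.** If both arms fail equally often with the same r, the two L terms cancel. If r = 0, the correction is zero. Either way the observed difference is 0.50 SD.

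**Case D: reversal.** If 5% fail in each arm but V correlates with Y only in the healthy arm (0.6 against 0), the observed difference is 0.5 + 0.6 × 0.109 = 0.565 SD. This pattern is contrived, but it shows that the direction is not guaranteed.

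**Effect on power.** At two-sided 0.05 (the plan sets 0.05 without stating sidedness), 63 per group gives 80% power for 0.5 SD. With SD held at 1 and before losing the subjects who fail, power is about 71% at 0.45 SD, 61% at 0.40 SD and 50% at 0.35 SD.

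**The case against.** A reader might infer that the most impaired subjects do drop out and that the disease effect is therefore understated. The documents do not support that as a statement of fact. They give no failure rates and do not link failure to vision. Failure could reflect handling of the joystick, or age. With no time or attempt limit stated for the visible stage, failures may be few.

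Enrolment also narrows the range. The first exclusion criterion removes subjects whose systemic or ocular condition may, in the investigator's opinion, prevent them from completing the tests. Glaucoma suspects must have normal visual fields, and AMD can be diagnosed on intermediate-size drusen alone. A failure rate of 20% to 30% in a mixed diseased group is therefore not an obvious central assumption.

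The restriction may also be deliberate. The probe outcome is described as a measure of spatial memory and navigation strategy, and requiring subjects first to be able to move is a reasonable control for that construct. It would be too strong to say that the design defeats the measurement of disability. Visual search ("The time and path to complete the task will be obtained") and the driving tasks are not described as subject to this check.

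It is also tempting to cite the later step, "Depending on the data obtained in this set of trials, the subject will be asked to continue with further tests of increasing difficulty", as a further source of bias. It comes after the probe trial and so cannot affect the probe outcome; the text does not say which results lead to harder tests.

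These arguments limit the size and certainty of the bias. They do not supply what is missing: a criterion for passing, a rule for those who fail, and a statement of the population to which the comparison applies.

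**Conclusion.** The point holds in conditional form. It is a stated selection rule without a criterion, combined with an analysis that by default includes only those selected. Attenuation is the likely direction if failure is commoner with worse vision and if visible-stage skill correlates similarly with the outcome in both arms. Neither condition is established by the documents.

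Of the two illustrations, 15% assumes equal effects of disease on the two stages and 29% assumes the larger 0.80 SD effect on the visible stage, so the second should not be quoted without that assumption. The concern is confined to the hidden-target and probe outcome and does not extend to the virtual reality battery as a whole. It should be corrected because the study sets out to measure disability and the correction is cheap.

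**What to change.** 1. Define the visible-stage proficiency criterion in advance, so that passing does not rest on the experimenter's judgement.
2. At each visit, log the stage reached and the reason for stopping. Recording of path and time is stated for the hidden-target trials but not clearly for the visible stage, and recording of reasons is not stated at all, so these data cannot be assumed to exist.
3. Report the proportion passing by arm as an outcome, using a logistic model adjusted for age.
4. Keep the planned comparison, but label it as applying to subjects able to move in the virtual environment.
5. Add a Mann-Whitney sensitivity analysis in which subjects who stop for performance reasons take the worst rank. Keep stops for motion sickness or by choice separate.
6. Apply the same rules at follow-up visits, where a patient may newly fail.

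The cost is a few sentences in the protocol, a little extra logging and one added analysis; the tests themselves do not change. The drawback is that the worst-rank result is a composite. It is harder to express in seconds, and it mixes the ability to move with spatial memory, which is why it should stand beside the completers' comparison and not replace it.

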****Amendment, Protocol version 1.21:**

All subjects will be compensated with \$30 for each scheduled or additional visit. Normal subjects will undergo 2 scheduled visits. An additional \$30 will be provided for participants who need 1 additional visit to complete all the tests. Subjects in the pathologies arms will undergo 14 visits in the first year of the study, 9 visits in the second and third years of the study, and 4 visits per year (2 visits every 6 months) until the end of the study, up to 5 years of participation. Additional \$30 per visit will be provided for participants who need additional visits to complete all the tests, up to a maximum amount of \$450/year.

CONSENT PROCESS

We will use protected health information to screen for possible/eligible subjects. No PHI will leave Duke. A member of the eye care team will approach the potential participant to introduce the study. Knowledgeable key personnel will explain the study to the potential subjects and the Principal Investigator will be available during the consenting process to answer any questions the potential subjects may have about the study. The consenting process will occur in a private room and no study related activities will begin until the subject's consent is obtained. Only delegated key personnel can consent potential subjects.

A waiver of consent and HIPAA authorization will be filed with the Duke IRB to allow us to review PHI and health information to screen potential participants.

A telephone script will be submitted to schedule potential subjects in Maestro Care for study screening prior to full consent, and in case subjects are interested in participating and they cannot discuss the study in person when they are initially seen, after the PI introduces the study and key personnel to them.

Subject's Capacity to Give Legally Effective Consent: Adult subjects able and willing to participate will sign the consent forms. If the vision of the potential subject is severely impaired enough to affect reading the consent document, the person obtaining consent, a study team member or a witness will read aloud and a witness will be required to sign the consent.

RISK/BENEFIT ASSESSMENT

Include a thorough description of how risks and discomforts will be minimized (per 45 CFR 46.111(a) (1 and 2)). Consider physical, psychological, legal, economic and social risks as applicable. If vulnerable populations are to be included (such as children, pregnant women, prisoners or cognitively impaired adults), what special precautions will be used to minimize risks to these subjects? Also identify what available alternatives the person has if he/she chooses not to participate in the study. Describe the possible benefits to the subject. What is the importance of the knowledge expected to result from the research?

Risks:

Risks from participating in the study are very low. The primary risks for all participants are some discomforts, which are similar to those encountered in any complete eye examination. Participants will undergo non-invasive procedures used for diagnostic purposes that are used in standard clinical care. The software for Macular pigment optical density analysis is currently undergoing FDA review and is not currently approved. The software for measurement of the trabecular meshwork stiffness (OCT/iFEM) from OCT is not currently approved. The OcuMet Beacon and Tono-Vera devices are currently undergoing FDA review and are not currently approved. The subject may experience mild discomfort due to drying of the eye during the study. Should a patient note drying, a drop of

artificial tears will be placed over the eye by the study key personnel. In very rare cases, artificial eye tear drops may cause irritation or allergy. There are no known risks associated with the psychophysics tests, EEG and eye tracking other than discomfort and fatigue. Subjects might become bored, fatigued or distressed while participating in the virtual reality and driving simulator tests. To minimize these potential effects, the tasks will be kept short and subjects will be instructed that they may request to interrupt the test anytime. The driving simulator, virtual reality tests, and balance assessment may cause dizziness or motion sickness in susceptible patients. Every precaution will be taken to minimize this possibility of motion sickness (e.g., by limiting the speed of linear or rotational motion). For the balance assessment task, falls will be prevented by the use of a harness system. All assessments, software, instruments that are not FDA approved will be used as tools to assess disability and device efficacy, and will not be used as a diagnostic procedure without confirmation of the diagnosis by another, medically established diagnostic product or procedure. There is, however, the potential risk of loss of confidentiality. Every effort will be made to keep the information confidential; however, this cannot be guaranteed. Some of the questions that will be asked as part of this study may make the patients feel uncomfortable. Patients may refuse to answer any of the questions and may take a break at any time during the study. Patient may stop their participation in this study at any time.

Unknown/Unforeseeable Risks

In addition to the risks and discomforts listed here, there may be other risks that are currently not known. Subjects will be informed if any other potential risk becomes known through the duration of the study. Also, the risks and discomforts may occur more often or be more severe than have been seen before and written in this form.

Benefits:

Subjects will be referred from the Duke Eye Center care providers after a comprehensive clinical eye examination from a routine visit. If the last clinical eye examination is not within 6 months of the study visit, the participant will be examined by the PI, with no additional cost to the patient. Participants will also undergo other tests that will allow a better understanding of the relationship between potential visual impairment caused by their diseases and the ability to perform daily tasks. The results of the study are likely to provide important information on how eye diseases are associated with visual impairment, task performance and quality of life. This may lead to development of better tests to predict patient performance and visual loss, which could benefit patients with these diseases.

COSTS TO THE SUBJECT

All procedures described here, including both visits, will be free of charge to patients. There is no additional cost for the subject if they participate in the study. Study related activities/procedures will be paid by the study.

DATA ANALYSIS & STATISTICAL CONSIDERATIONS

Describe endpoints and power calculations. Provide a detailed description of how study data will be analyzed, including statistical methods used, and how ineligible subjects will be handled and which subjects will be included for analysis. Include planned sample size justification. Provide estimated time to target accrual and accrual rate. Describe interim analysis including plans to stop accrual during monitoring. Phase I studies, include dose escalation schema and criteria for dose escalation with definition of MTD and DLT.

For all test results and variables, an extensive data preparation will be performed, with analysis of distributions, error checking and cross-tabulation. We will investigate differences in the results of the tests between diseased and healthy participants. Normality of variables will be assessed using histograms and Shapiro-Wilk tests. Student t tests will be used for comparison of means of normally distributed variables, whereas Mann-Whitney tests will be used for non-normally distributed variables. Generalized estimating equations (GEE) will be used to take into account potential correlations between tests results from the two eyes of the same subject.

Mixed models will be used for analysis of longitudinal data collected over time. These methods can successfully take into account longitudinal correlations among observations as well as correlations of results of eyes nested within patients. We will also use methods such as survival analysis (Weibull and Cox models) to assess prediction and joint longitudinal survival models.

All statistical analyses will be performed by [name] and associates using commercially available statistical and mathematics software Stata (version 15; StataCorp LP, College Station, TX, USA), MATLAB (Mathworks, Inc.), and MPLUS (Muthen & Muthen). Additional analysis and image processing from de-identified data will be performed by GA Tech's PI [name], and [name] and associates. An alpha level will be generally set at 0.05, unless there is a need to correct for multiple comparison testing which will then be performed by procedures such as false discovery rate.

